Subjective cognitive measures of the Metamemory in Adulthood (MIA),⁴⁹ and Memory Function Questionnaire (MFQ),⁵⁰ will be administered. The MIA 108-item test is used to describe memory issues and changes relevant to healthy aging, and assess impact of disclosure of perceived cognitive symptoms and abilities.⁴⁹ The MFQ 64-item test reflects subjective appraisals of frequency of forgetting in different situations, the

seriousness of the consequences of forgetting in these situations, comparison of present and past memory functioning, and frequency of memory strategy use; and assesses the impact of disclosure of perceived cognitive symptoms and abilities.⁵⁰

Behavioral health measures obtained at baseline also include: 1) a measure for quality of life, the SF-12 Physical and Mental Health Summary Scale – a 12-item multi-purpose short form (SF) generic measures of health status, and self-rated overall physical and mental health⁵¹; and 2) a measure of how individuals view their future with the Future Time Perspective Scale – a 10-item scale to assess future time perspective as a developmental construct in adults.⁵²

Measures of recall and comprehension, behavioral changes, information sharing and interpersonal relationships, willingness and effort to participate, and cognitive symptoms will be created for this study. Participants will take these created health behavior surveys at baseline and at the 6-week and 6-month follow-up visits (Visits #5 and Visits #6, respectively) to determine the type and frequency of behavior changes in response to learning risk information. Information collected will include assessing health behavior changes, advanced planning, insurance changes (i.e. purchasing or altering long-term care policies), medication changes, willingness to enroll in clinical research, stigma, and tolerance of research risk.

An Emergency Contact Information sheet will be completed by the participant, including two personal emergency contacts and one physician contact. In the event that the participant experiences significant study-related distress, the study team may disclose to an emergency contact that the participant is enrolled in the study. Amyloid status will not be disclosed by the study team.

In addition, Dynamic Experiments for Estimating Preference (DEEP)⁶¹ behavioral assessments will measure participant risk and time preference as presented electronically through various decision-making scenarios.

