Primary Analysis 1.1: For this aim we focus on one outcome, ADCS-PACC, and thus use an alpha level of 0.05 to determine statistical significance. First, we will obtain descriptive statistics for those who are in the D+ and D- groups among A+ subjects. Then, we will compare ADCS-PACC scores between D+ and D- groups among A+ subjects using a two-sided test of means. Next, we will compare D+ and D- groups on potential confounders. We will initially consider confounders due to the Covid-19 pandemic (as described below) and then consider other confounders (including age, education, premorbid function, experiences of discrimination). If any are significantly different between the two groups ($p < 0.05$), despite randomization, we will conduct regression analysis adjusting for those confounders that are different. Analyses will be repeated measures (6 wks. and 6 mos.) adjusting for baseline measure at time of randomization. We will focus on 6 month differences, but also check for time-averaged differences between D+ and D- groups. Check ADCS-PACC for normality. If normal, linear regression analysis for repeated measures can be used, specifically a mixed-effects model with repeated measures (MMRM). If not normal, we will use an appropriate transformation to make the distribution more normal. We will also conduct an Intention-to-Treat (ITT) analysis, which will incorporate information from those who drop out over the 6 months, assuming missing at random. This analysis will have better control of type 1 error and power. We will model time as a categorical measure, and the primary outcome will be the estimated difference (contrast) between the two groups (D+ and D-) at 6 months and secondarily the time-averaged difference. We will also apply a model with 3 repeated measures (baseline, 6 wks., 6 months) without adjustment for baseline ADCS-PACC to examine the full trend over time, but this will be a secondary analysis.

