Exploratory Analysis 1.3: The analysis will be the same as the primary analysis, but now conducted only in the African Americans in the study. If the hypothesis is true, we expect a larger difference, but the study is not powered for this subgroup analysis. To formally test whether African Americans have a greater response, we will perform analyses of the full group of A+ individuals, adding an interaction term to the model for race * disclosure group.

Aim 2: To determine whether disclosure of elevated brain amyloid will cause psychological distress.

Study Subjects: All Study Participants and the subgroup of A+ subjects

Outcomes: IES (Impact of Event Score), measured twice (6 wks., 6 mos.), and INI-AD, measured twice (6 wks., 6 mos.)

Hypothesis 2.1: At 6 weeks after disclosure, A+D+ participants will have greater IES scores and INI-AD scores than A-D+ or D- participants.

Analysis 2.1: Analysis will generally use the same methods as Aim 1. For this Aim, IES is the primary outcome for which we will use an alpha level of 0.05. INI-AD is a secondary outcome. Our main focus for this aim is contrasting scores between the A+D+ and A-D+ groups. We will also contrast the A+D+ and the D- groups (as long as the A+D- and A-D- exhibit similar outcomes). As in Aim 1, we will obtain

descriptive statistics between the two groups (A+D- and A-D+ for the first contrast and then A+D- vs the D- group). We will also evaluate the confounding effect of Covid-19 as described in Aim 1 and subsequently other potential confounders for these contrasts and incorporate if needed in further regression analyses. Note that there is no IES at baseline. So there is no adjustment for a baseline measure. The same holds true for INI-AD. One major difference here is that the IES and INI-AD are not normally distributed and cannot be transformed to become so. Thus, we will use generalized linear models fit with generalized estimating equations using a log link and a gamma distribution. If needed, we will add a value of 1 to all scores to shift the distribution away from zero and use a log transform on the data. We will focus on the differences at 6 weeks, but also evaluate the time-averaged differences.

Exploratory Hypothesis 2.2: Comparison of outcomes at 6 weeks and 6 months after disclosure will show African Americans to be equally vulnerable to psychological distress as measured by IES and INI-AD after amyloid imaging compared to all other racial and ethnic groups.

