Aim 3 Analyses: While we will examine each measure individually, our primary analysis will focus on aggregate summary measures for: 1) any preventative health behavior changes made over 6 months since disclosure that the participant reports, and 2) any advanced planning measures taken over the 6 months since disclosure. Separate bivariate analyses will be conducted for each of these summary measures. For 1) and 2), we will contrast the D+ and D- groups using chi-square statistics. We will also contrast the summary measures in the disclosed group by those with elevated and not elevated brain amyloid. We will conduct multivariable logistic regression analyses to control for any variables that appear to be confounders. We will use follow-up analyses to elucidate factors driving significant main effects.

For 3) Well-being, we will examine group differences in each stigma, quality of life and relationships, sharing of information at 6 months post disclosure. We will examine mean differences between groups on two measures of stigma (AD concern since learning risk/amyloid & Social Impact Scale) and conduct outlier analyses to identify potential predictors of extreme responses. We will use ordinal logistic regression to examine differences in quality of life as measured by an estimate of the impact of risk estimate/PET. To examine relationships and result sharing, we will use two-stage models to examine (a) decisions to share with others and (b) levels of satisfaction with this sharing. Analyses of decisions to share information will include a participant's sharing of each a risk estimate and an amyloid test result. Binary outcomes will be examined using unadjusted proportions and adjusted odds ratios. Analyses of satisfaction will include rank ordered levels of satisfaction with decision to share, of sharing a risk estimate, and of sharing an amyloid result. We will contrast groups defined by disclosure and amyloid status.

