Adjusted models will control for measured factors unbalanced across study groups and baseline values will be assessed as predictors of Aim 3 outcomes. All Aim 3 analyses will be conducted in the full group and also in the subgroup of disclosed study participants. Prior to analysis we will check that all model assumptions are adequately met. If not, we will adjust the analysis plan accordingly. Since these are exploratory analyses, we will use an alpha level of 0.05 to assess statistical significance. We will report estimates and their respective 95% confidence intervals.

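### Aim 3 does not prespecify the related Visit 2 survey value as a covariate in its group contrasts; covariates enter by imbalance or apparent confounding

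*SAP*

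**What the plan says.** The Protocol (section V, Step 5, Visit #2) states: "Participants will take these created health behavior surveys at baseline and at the 6-week and 6-month follow-up visits". It lists health behaviours, advance planning, insurance, medication changes and stigma among the topics. Visit 2 comes before the scan and randomisation (Step 7) and disclosure (Step 8).

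For the two summary measures, any preventive behaviour change and any advance planning, the SAP (Aim 3 Analyses) says: "For 1) and 2), we will contrast the D+ and D- groups using chi-square statistics". It then adds: "We will conduct multivariable logistic regression analyses to control for any variables that appear to be confounders". For stigma: "We will examine mean differences between groups on two measures of stigma (AD concern since learning risk/amyloid & Social Impact Scale". For quality of life it plans "ordinal logistic regression to examine differences in quality of life as measured by an estimate of the impact of risk estimate/PET". Sharing of results gets unadjusted proportions and adjusted odds ratios.

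On baseline, the closing paragraph of Aim 3 says: "Adjusted models will control for measured factors unbalanced across study groups and baseline values will be assessed as predictors of Aim 3 outcomes". Aim 3 is labelled exploratory and tested at 0.05, with 95% confidence intervals.

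Elsewhere the SAP is explicit. For the PACC (Primary Analysis 1.1): "Analyses will be repeated measures (6 wks. and 6 mos.) adjusting for baseline measure at time of randomization". For the IES (Analysis 2.1): "Note that there is no IES at baseline. So there is no adjustment for a baseline measure".

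**The concern.** No sentence places an outcome's Visit 2 counterpart in its D+ versus D- or A+D+ versus A-D+ model. A covariate gets in if it looks unbalanced or looks like a confounder.

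For D+ versus D- that is the wrong test of usefulness. A baseline value improves precision because it predicts the outcome, and randomisation tends to balance exactly such a value, so the rule usually drops it.

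For A+D+ versus A-D+ the issue is different. Amyloid status is not randomised, so earlier behaviour and earlier planning are candidate confounders. A check for visible imbalance can miss a difference large enough to matter.

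Advance planning adds a further problem. Someone who already holds an advance directive at Visit 2 can hardly complete a new one, yet counts as a no on that item.

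**Working it through.** **Inputs from the documents.** 370 enrolled and about 10% dropout (Protocol, Power Calculation); 1:1 allocation (Protocol, Step 7); A+ share between 25% and 30% (SAP, the Analysis 1.1 paragraph on a sample-size shortfall); alpha 0.05 (SAP, Aim 3), taken as two-sided. Completers: 370 × 0.9 = 333, or about 166 per arm. With an assumed 28% A+, the disclosed arm has 0.28 × 166 ≈ 47 A+D+ and 119 A-D+.

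**The plan's own figure.** Aim 3 has no stated power, event rate, SD or baseline correlation. The only current power figure is for Aim 1 (50 per group, difference 1.25, SD 2.2, 80%). It reproduces: 2 × (2.80 × 2.2 / 1.25)² ≈ 49 per group. It does not bear on Aim 3, so everything below rests on assumed inputs.

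**Step 1: which outcomes have a Visit 2 counterpart?**

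| Aim 3 outcome | Counterpart at Visit 2 |
|---|---|
| Any behaviour change since disclosure | Not the same measure; related status (current behaviour) |
| Any advance planning since disclosure | Not the same measure; related status (existing directive or policy) |
| Social Impact Scale | Possibly; the Protocol lists stigma but does not name the scale |
| AD concern since learning risk or amyloid; impact of risk estimate/PET; sharing and satisfaction | None |

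The SF-12 has a baseline, but it is not the quality-of-life measure that the SAP names.

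**Step 2: D+ versus D-, binary outcome (simulated, 166 per arm).** Assumed: baseline status present in 50%, comparison rate 50%, conditional odds ratio (OR) for disclosure 2.0. With a baseline-outcome OR of 4, the comparison rates are 66.7% and 33.3% (mean 50%). An OR of 2 turns these into 80% and 50% (mean 65%), a difference of 15.0 points. The other rows follow in the same way.

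| Baseline OR | Marginal difference | Unadjusted power | Adjusted power | Gain |
|---|---|---|---|---|
| 2 | 16.2 points | 85% | 86% | under 1 point |
| 4 | 15.0 | 80% | 84% | 4 |
| 9 | 12.9 | 67% | 77% | 10 |
| 16 | 11.1 | 55% | 71% | 16 |

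The fall down the unadjusted column comes largely from holding the conditional OR fixed while the marginal difference shrinks. Only the gain within a row measures what adjustment buys. Repeat simulations move these gains by about 2 points.

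A second set holds the marginal rates fixed and uses a continuous baseline with OR per SD of 1.35, 1.82, 2.72 and 4.48:
- 45% vs 30%: 81.2 to 82.0, 79.8 to 82.9, 81.0 to 87.3, 80.2 to 91.2. Gains 0.8, 3.1, 6.3 and 11.0 points.
- 15% vs 6%: 78.6 to 79.0, 78.1 to 80.0, 78.4 to 82.1, 78.2 to 86.0. Gains 0.4, 1.9, 3.7 and 7.8 points.

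With a 10% comparison rate, conditional OR 2.5 and baseline OR 4 to 16, the gain is about 2 to 7 points.

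**Step 3: D+ versus D-, continuous score, if the same scale was given at Visit 2.** ANCOVA multiplies the variance by 1 − ρ². The unadjusted detectable difference at 80% power is 2.80 × √(2/166) ≈ 0.308 SD. With ρ = 0.3, 0.5 and 0.7 the factor is 0.91, 0.75 and 0.51, the detectable difference is 0.293, 0.266 and 0.220 SD, and power at 0.308 SD is 83.6%, 89.9% and 97.5%.

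**Step 4: A+D+ versus A-D+.** Suppose imbalance is judged at p < 0.05, as in Aim 1; Aim 3 gives no criterion. For a baseline status near 50%, the standard error of the difference is √(0.25/47 + 0.25/119) = 0.086. The observed imbalance must then exceed 1.96 × 0.086 ≈ 17 points to be flagged, so a true 15-point difference would be missed more often than not. With the Step 2 comparison rates, such a difference alone would create an apparent effect of 0.15 × (66.7 − 33.3) = 5.0 points at baseline OR 4, or 0.15 × (75 − 25) = 7.5 points at OR 9.

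**Step 5: advance directive item.** Assume 15% vs 30% among those without a directive at Visit 2. If 30%, 50% or 70% already had one, the difference over everyone is 15 × (1 − share) = 10.5, 7.5 or 4.5 points. Variance and usable n also change, so power is the fair comparison: 75.0% for everyone against 78.5% among those without one (116 per arm), 58.1% against 64.1% (83 per arm), and 37.2% against 43.4% (50 per arm). The gain is about 4 to 6 points.

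**The case against.** A reader might infer that Aim 3 rests on unadjusted tests alone. It does not: logistic, ordinal logistic and adjusted odds-ratio analyses are planned, and the sentence on baseline values can be read as making them candidate covariates. What stands against the plan is that their role is ambiguous and not fixed in advance.

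A reader might also infer that the SAP breaks its own rule of adjusting for baseline wherever one exists. There is no such rule. The two subjective memory questionnaires are given at Visit 2, yet Secondary Analysis 1.2 plans MANOVA and ANOVA with no baseline term mentioned. Only the PACC has explicit adjustment.

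The two summary measures count events since disclosure, so they have no baseline of the same measure. The survey forms are not in the documents, so whether Visit 2 records existing directives or policies has to be checked. The directive example is one item; a person with a directive can still score a yes on any planning through insurance.

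Finally, the D+ versus D- hypotheses for behaviour and planning are of equivalence or similarly low frequency, with no margin, so power to detect a difference is not exactly the question asked. Aim 3 is also exploratory. Both points lower the stakes. Neither is a reason to choose covariates by imbalance when the relevant ones can be named beforehand.

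**Conclusion.** The point holds in a limited form. The main Aim 3 contrasts do not prespecify the related Visit 2 value, and the rule for adjusted models usually leaves out a prognostic but balanced one.

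For D+ versus D- nothing in the documents supports a claim of bias: unadjusted tests of randomised arms are valid, and the loss is precision. Its size depends on event rates and baseline strength that the documents do not give. Under the assumptions shown, it runs from near nil for a weak predictor to about 15 points of power for a very strong one, and about 2 to 7 points for an uncommon outcome. The SAP expects advance planning to be infrequent, so the lower range is the more relevant one there.

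For A+D+ versus A-D+ the concern is confounding that escapes notice. The planned confounder adjustment reduces it but does not guarantee that prior behaviour or planning is included.

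**What to change.** For each Aim 3 outcome, state in the SAP whether a Visit 2 counterpart exists: the same scale, or a related status such as current behaviour, an existing directive or an existing policy. Then:

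- Where a counterpart exists, include it as a fixed covariate in the D+ versus D- and A+D+ versus A-D+ models regardless of balance: logistic regression for the two summary measures, ANCOVA for a stigma score that was given at Visit 2.
- Keep the unadjusted chi-square or mean difference as supportive.
- Tabulate separately the participants who already had a directive or long-term care policy at Visit 2.
- Give no baseline covariate to outcomes that exist only after disclosure: AD concern since learning risk or amyloid, impact of the risk estimate/PET, sharing, and satisfaction with sharing.

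The cost is SAP wording plus a check of what the Visit 2 forms recorded; no new data are needed. If Aim 3 results by group have already been seen, report the adjusted models as added afterwards.
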